## 2. TEAM STUDY SUMMARY

**Title** An open label, randomised, comparative trial of 5 years adjuvant exemestane treatment versus 2.5-3 years adjuvant tamoxifen followed by exemestane treatment in postmenopausal women with early breast cancer.

**Study objectives**

**Primary endpoint**

- ❑ Disease Free Survival (DFS)

**Secondary endpoints**

- ❑ Overall Survival (OS)
- ❑ Incidence of second breast cancer (in contralateral breast)
- ❑ Safety and long-term tolerability of both regimens

Differences in outcome based on pathological subgroups will also be analysed and a quality of life (QOL) comparison between the two study arms undertaken (using the FACT-ES questionnaire).

[figure not shown]
**Study design** Phase III, open label, randomised, multicentre, international trial.

**Subject numbers** 8740 subjects globally, 1240 from the UK/ROI.

**Main selection criteria** Women with a histological/cytological diagnosis of early invasive breast carcinoma, completely resected, and who meet the following criteria:

- ❑ Postmenopausal
- ❑ ER/PgR-positive
- ❑ - Any node-positive cancer
  - Any cancer  $\geq$  3cm
  - Node-negative cancer, grade II or III and  $\geq$  1cm
- ❑ Adequate haematological, renal and hepatic function
- ❑ ECOG performance status 0, 1 or 2
- ❑ Patients must be randomised within 10 weeks surgery or completion of chemotherapy

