### 6.1. Treatment

Treatment must begin within 5 working days after the patient's registration on the study and within 10 weeks of completion of surgery, +/- chemotherapy. Radiotherapy should be given according to local policy.

Subjects will be randomised 1:1 to receive either:

- Tamoxifen, 20mg once daily, until completing at least 2.5 years therapy. Patients will switch to exemestane before completing 3 years of tamoxifen and then complete a total of 5 years endocrine therapy (treatment arm A)

**or**

- Exemestane, 25 mg once daily, for a minimum of 5 years (treatment arm B)

Both study drugs are registered for breast cancer and will be prescribed by the Investigator. Ongoing studies may provide important information regarding the optimum duration of endocrine therapy. It is therefore proposed to review these data as they emerge and formulate a recommendation for treatment following the 5-year time period. The possibility of a second randomisation may be appropriate.

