### 15.2. Hypothesis and sample size

In the amended protocol (27th October 2004), patients in the tamoxifen arm are assumed to switch to exemestane after 2¾ years (range from 2½ -3 years) of treatment with tamoxifen. The main goals of this study are to compare the DFS among patients who received either exemestane 25 mg or tamoxifen for 2.5- 3 years followed by 2.5- 2 years of exemestane for 2.75 years (i.e. 33 months), and for 5 years. Overall survival and DFS at 10 years will be evaluated. The safety for both arms at 2.75 years and 5 years will also be assessed.

The ATAC paper provided updated information comparing tamoxifen and anastrozole. The 3-year DFS rate was estimated to be approximately 90% for the tamoxifen arm (i.e., Arm B before switch). If the hazard ratio of DFS is assumed to be 1.28 between the two treatment arms (Arm B / Arm A), **723 events** will achieve 87% power to detect the corresponding difference in DFS with a two-sided significance level of 0.0298. Assuming constant exponential rates in both groups with a hazard ratio of 1.28), **9300 patients (4650 in each group) are sufficient in order to observe these 723 events after each subject is followed for 2.75 years.** The Independent Data Monitoring Committee, as part of their evaluation of the progress of the trial, will review an interim analysis at the time 50% of the events are reported for the first co-primary endpoint, at or before 2.75 years from the time of randomization.

The entire TEAM trial will accrue a total of 9300 patients in order to observe 723 DFS events at 2.75 years (33 months). UK will contribute approximately 1200 patients.

**Timing of the first primary analysis of DFS:** approximately 2¾ years after the last patient has been enrolled when there will be at least 723 events. Based on this, the following hypotheses are stated:

**A:** under the null-hypothesis ( $H_0$ ) if there is no difference between the two treatments, assuming the 3-year DFS is 90%, then: treatment arm A (tamoxifen) and treatment arm B (exemestane) will show a 3 years DFS of 90%.

**B:** under the alternative hypothesis ( $H_1$ ) the HR is 1.28 for the first 2¾ years and hence ( $H_0$ ) is rejected.

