### **15.6. Interim Analysis**

The entire TEAM trial will accrue a total of 9300 patients in order to observe 723 DFS events in the first co-primary endpoint at 2.75 years. Safety analyses will be reported to the Independent Data Monitoring Committee (IDMC) every 6 months without evaluation of efficacy. The number of efficacy events will be monitored centrally every 3 months and reported to the IDMB. One interim efficacy analysis is planned for the first co-primary endpoint, to be reviewed by the IDMC. As part of their evaluation of the progress of the trial, they will review an interim analysis of the combined TEAM trial at the time 50% of the events are reported for the first co-primary endpoint, at or before 2.75 years from the time of randomization when half of the required number of DFS events for the first co-primary endpoint have occurred. These unblinded data will only be reviewed by IDMC members. The primary objective of the interim analysis is the early detection of either alarming side effects, intolerability to the treatment regimens, or of large differences in treatment effects.

The overall alpha-level for the first co-primary analysis will be maintained at 0.0302 using an O'Brien-Fleming-type alpha-spending function. The levels of significance at the interim analysis and at the final analysis for the first co-primary endpoint are 0.0012 and 0.0298, respectively.

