Tamoxifen is firmly established as an effective adjuvant therapy for women after treatment for early stage breast cancer. Randomised trials have established that adjuvant tamoxifen taken for five years reduces the risk of breast cancer recurrence by 40% in women with tumours expressing significant levels of oestrogen receptor. Emerging data from randomised clinical trials indicates a role for the new third-generation aromatase inhibitors, which inhibit oestrogen synthesis rather than antagonise at the receptor level. The Anastrozole, Tamoxifen Alone or in Combination study (ATAC) has compared 5 years of anastrozole with 5 years of tamoxifen and has shown a reduction in risk of relapse by 22% with immediate use of anastrozole alone in hormone receptor-positive cancers. The published results have not analysed survival and a survival analysis is expected soon. In the UK anastrozole is currently only licensed for women with early breast cancer where tamoxifen is contraindicated. The main concern with adjuvant anastrozole being loss of bone mineral density compared to tamoxifen, with an associated significant but small increase in fractures observed. Another third-generation aromatase inhibitor exemestane has been examined in a different trial design, the Intergroup Exemestane Study (IES), where women with early breast cancer completing between 2 and 3 years of tamoxifen were randomly allocated to complete a standard 5-year course of tamoxifen or to switch to exemestane. This study demonstrated an advantage in favour of the aromatase inhibitor in reducing risk of relapse in oestrogen receptor-positive women by 36%. There are therefore two competing strategies, aromatase inhibitor from the outset and a sequential approach. Which strategy is the most effective is currently unknown.

In the **TEAM** study women with receptor-positive early breast cancer are randomised to treatment with tamoxifen for 2.5-3 years followed by exemestane to complete 5 years of treatment or treatment with exemestane for 5 years.

This trial is a multinational, multicentre, trial with a recruitment target of 8740 patients. The trial is being run from the Cancer Research UK Clinical Trials Unit in Birmingham for UK participants. The primary endpoint for the study is relapse-free survival with secondary endpoints of overall survival and tolerability. We have completed a quality of life analysis and will also be performing a pathological correlate study.

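### The protocol gives two global recruitment targets (8740 and 9300), and section 15.2 labels the tamoxifen arm both A and B, so the direction of the planned hazard ratio is inconsistent

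*Protocol*

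**What the plan says.** **Recruitment target.** The study summary (section 2) gives "8740 subjects globally, 1240 from the UK/ROI". The GP letter for new patients says "This trial is a multinational, multicentre, trial with a recruitment target of 8740 patients". Section 15.2 says "The entire TEAM trial will accrue a total of 9300 patients in order to observe 723 DFS events at 2.75 years (33 months"), and section 15.6 repeats the number: "The entire TEAM trial will accrue a total of 9300 patients in order to observe 723 DFS events in the first" co-primary endpoint. For the national share, section 15.2 says "UK will contribute approximately 1200 patients". All of this is current text; none of it sits in an amendment log. Section 4 says recruitment will continue to a new global target but does not give the number.

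**Arm labels.** Section 6.1 makes the tamoxifen-first arm A and defines the other as "Exemestane, 25 mg once daily, for a minimum of 5 years (treatment arm B"). In section 15.2, hypothesis A follows the same labels: "treatment arm A (tamoxifen) and treatment arm B (exemestane) will show a 3 years DFS of 90" per cent. The sample-size paragraph of the same section does the opposite. It gives the 90% rate for the tamoxifen arm and identifies that arm in parentheses as Arm B. The next sentence says the "hazard ratio of DFS is assumed to be 1.28 between the two treatment arms (Arm B / Arm A"). Hypothesis B then states a hazard ratio of 1.28 without naming arms.

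**The concern.** A sample size should appear once, with one value. Here the two places most likely to be read by people outside the statistics group carry a different number from the section that derives it. The choice matters more than usual because section 14.1 censors event-free patients at 2.75 years for the first co-primary endpoint. Once every patient has reached 2.75 years, the event count is fixed by the number enrolled. In most event-driven trials a small shortfall is cured by waiting, but not in this one.

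The labelling problem affects how the primary hypothesis is read. A ratio given as B/A means opposite things under the two labellings that section 15.2 uses. Anyone programming or reporting the ratio from that section has to guess which one applies.

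**Working it through.** **1. Reproduce the plan's event number.** Inputs from section 15.2: hazard ratio 1.28, two-sided alpha 0.0298, power 87%. Section 6.1 gives 1:1 allocation. The normal quantiles are 2.1727 (for 1 − 0.0149) and 1.1264 (for 0.87); their sum squared is 10.884.

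- Schoenfeld: 4 × 10.884 / (ln 1.28)² = 43.54 / 0.06094, or 715 events.
- Freedman: 10.884 × (2.28 / 0.28)² = 10.884 × 66.31, or 722 events.
- Power at 723 events: 87.4% (Schoenfeld), 87.1% (Freedman).

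The stated 723 events and 87% power therefore reproduce.

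**2. Expected events by 2.75 years**, with exemestane the better arm and no loss.

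- Tamoxifen hazard: −ln(0.90)/3 = 0.03512 per year.
- Exemestane hazard: 0.03512 / 1.28 = 0.02744 per year.
- Failure by 2.75 years: 1 − exp(−0.03512 × 2.75) = 0.09206 on tamoxifen and 1 − exp(−0.02744 × 2.75) = 0.07268 on exemestane; sum 0.16474.
- 9300 patients: 4650 × 0.16474 = 766 events.
- 8740 patients: 4370 × 0.16474 = 720 events.
- Patients needed for 723 events: 2 × 723 / 0.16474 = 8778.

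So 9300 leaves room for (9300 − 8778)/9300 = 5.6% of patients contributing no events, while 8740 is 38 patients short before any loss.

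**3. Power at those counts** (Schoenfeld, alpha 0.0298): 87.3% at 720 events, 87.4% at 723, 89.3% at 766.

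**4. Sensitivity to loss.** The protocol states no loss rate, so these are assumptions. If lost patients contribute no events, 5% loss gives 728 events (9300) or 684 (8740), and 10% loss gives 689 or 648. If they contribute half their expected events, 10% loss gives 728 or 684.

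**5. Direction of the ratio.**

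| Labelling | B/A = 1.28 means | Exemestane 3-year DFS (tamoxifen 90%) | Patients for 723 events |
|---|---|---|---|
| Sample-size paragraph of 15.2 (tamoxifen = B) | tamoxifen / exemestane | 0.90^(1/1.28) = 92.1% | 8778 |
| Section 6.1 and hypothesis A (tamoxifen = A) | exemestane / tamoxifen | 0.90^1.28 = 87.4% | 6941 |

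In the second row the exemestane hazard is 0.03512 × 1.28 = 0.04495 and the failure probabilities sum to 0.20835. Then 2 × 723 / 0.20835 gives 6941 patients, and 9300 patients would give 4650 × 0.20835 = 969 events. Only the first row brings the required number near 9300. The event formulae give the same answer for 1.28 and 1/1.28.

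**The case against.** Several points on the other side are fair.

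- **The shortfall is tiny.** Three events in 723 is 0.4%, and it rests on a control rate that section 15.2 itself calls approximate. If the count is Poisson with mean 720, the chance of reaching 723 is still about 46%. This stands: 8740 would not certainly miss the target, and a reader who inferred that it leaves the trial underpowered would be wrong, since 87.3% still meets the stated 87%.
- **The statistical section governs.** It gives 9300 consistently and ties it to the event count, while 8740 appears only in a synopsis line and a letter. This reduces the practical risk but does not remove the contradiction.
- **The national figures may agree.** One covers the UK and the Republic of Ireland, the other the UK alone and only approximately. Both can be true, so this is a matter of scope and not a shown conflict.
- **The ratio has a local definition.** A reader might infer from the section 6.1 labels that the trial was planned with exemestane as the worse arm, or that the alternative hypothesis opposes the objective of improving DFS. The documents do not support either. The sentence just before the ratio labels tamoxifen as Arm B, which gives the intended direction; hypothesis B names no direction; and only that direction is close to 9300 patients. What remains is a swapped label.

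**Conclusion.** Two inconsistencies hold. First, the global target is 8740 in the summary and GP letter and 9300 in section 15. On the plan's assumptions with no loss, 9300 meets the 723-event requirement (about 766 expected). At 8740 the expected count is about 720, marginally below it, and censoring at 2.75 years rules out recovery by waiting. Before loss the effect on power is about a tenth of a percentage point. Any larger effect depends on a loss rate that the protocol does not give. By the same token, whether 9300 suffices after loss depends on that rate.

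Second, section 15.2 labels tamoxifen both B and A, so the direction of its hazard ratio is inconsistent within the section. This changes neither the 723 events nor the 87% power, and it is not evidence that exemestane was assumed to be inferior.

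**What to change.** - In the study summary and the GP letter for new patients, replace 8740 with 9300.
- State whether the national figure is for the UK or for the UK and the Republic of Ireland, and use that scope in both section 2 and section 15.2.
- In the sample-size paragraph of section 15.2, change the parenthetical label of the tamoxifen arm from Arm B to Arm A.
- In that paragraph and in hypothesis B, write the ratio by drug name: tamoxifen-first over exemestane = 1.28.

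The cost is a wording amendment through the route in section 17.3 and a corrected letter. No patients are added, because 9300 is already the target in section 15, and the event number, alpha and power stay as they are.

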### Patients who fulfill the eligibility criteria

### **RANDOMISATION**

(Mon- Fri, 9am-5pm)

### **3. BACKGROUND AND INTRODUCTION**

#### **Preface**

The *TEAM* trial was designed in 2000/2001 and commenced recruitment in December 2001. The original trial design was to compare tamoxifen for 5 years with exemestane for 5 years in postmenopausal women with early breast cancer. Since the start of the trial a large body of information regarding third-generation aromatase inhibitors in early breast cancer has emerged and in particular data has been published demonstrating a clear Relapse Free Survival (RFS) advantage to a sequential strategy in which exemestane is introduced after 2-3 years of prior tamoxifen. As a result of this data a protocol amendment has been introduced in which patients originally randomised to tamoxifen will be recommended to switch to exemestane after 2.5-3 years of tamoxifen therapy. This protocol has been amended to incorporate this change and contains information concerning the introduction of this protocol change for existing patients recruited to the original trial design and information regarding the conduct of the trial for new patients. The new protocol also contains a number of additional revisions to update the trial conduct in accordance with recent changes in research governance.

#### **3.1. Background - Tamoxifen**

Tamoxifen has for many years been the standard hormonal treatment for postmenopausal women following complete resection of primary oestrogen receptor (ER) positive breast cancer. The Early Breast Cancer Trialists' Collaborative Group (EBCTCG) has performed a meta-analysis of the randomised trials of adjuvant tamoxifen and unequivocally demonstrated the advantage of tamoxifen in improving relapse free and Overall Survival (OS) in women with ER-positive early breast cancer. The magnitude of the benefit increases with increasing duration up to 5 years. Five years of adjuvant tamoxifen reduces risk of recurrence by 47% and risk of breast cancer death by 26%. This finding is supported by randomised comparisons of 2-3 years vs. 5 years of adjuvant tamoxifen, which show a further 18% reduction in risk of relapse when tamoxifen is continued for more than 2-3 years. The impact on survival in these trials requires longer term follow-up but trends towards a survival advantage are seen.

Three trials that were designed to investigate duration of tamoxifen beyond 5 years have now reported early results. However, the results thus far are contradictory and therefore controversial. The largest study, The National Surgical Adjuvant Breast and Bowel Project (NSABP) B14 trial in node negative patients shows a significant better RFS and OS for the 5 year treatment. The Scottish trial shows a non-significant trend towards better outcome for the 5 year treatment in a population of node-positive and node-negative patients. In contrast the Eastern Cooperative Oncology Group (ECOG) trial has reported a benefit for continued tamoxifen. Further trials are still ongoing which will, in due course, provide definitive information as to the optimal duration of tamoxifen. Based on the current evidence, 5 years of tamoxifen is considered the standard duration of adjuvant tamoxifen monotherapy treatment for postmenopausal patients.

#### **3.2. Background – Third-generation aromatase inhibitors**

Tamoxifen acts as a competitive inhibitor of oestradiol, binding directly to the oestrogen receptor (ER), where it acts as a partial agonist. The predominant action in oestrogen-sensitive breast cancer is antagonistic but partial agonist activity is clinically important in postmenopausal women, since it results in preservation of bone mineral density and has a favourable effect on lipid profile. There are however negative aspects to the partial agonist effects since these result in endometrial stimulation. Endometrial pathologies are more common with tamoxifen which leads to adverse gynaecological symptoms such as vaginal discharge, increased incidence of postmenopausal bleeding and increased incidence of endometrial cancer.

An alternative strategy to oestrogen antagonism is to deplete circulating oestrogen levels. Aromatase inhibitors act systemically to inhibit oestrogen synthesis in tissues. These compounds prevent oestrogen biosynthesis by inhibiting the aromatase enzyme, which catalyses the conversion of adrenal and ovarian androgens to oestrogens. Aromatase is most active in adipose, liver and breast tissues. The first aromatase inhibitor, aminoglutethimide (AG), was introduced in the 1970s. Although this first-generation aromatase inhibitor was effective as an adjuvant therapy in breast cancer, it was poorly tolerated and was replaced by the well-tolerated second-generation aromatase inhibitor 4-OH-androstenedione (formestane). This compound however only suppresses plasma oestradiol to a third of baseline levels and requires parenteral administration. Some years later, third-generation aromatase inhibitors were developed. They fall into two principal categories (a) non-steroidal, exemplified by fadrozole, vorozole, letrozole and anastrozole and (b) steroidal, exemplified by exemestane, (reviewed in). Of these only anastrozole, letrozole and exemestane are commercially available for the treatment of advanced breast cancer. All three drugs have been evaluated as second-line treatment for advanced breast cancer and all have significant advantages to the comparator drug, megestrol acetate, and have become established as endocrine agents of first choice in the treatment of tamoxifen-resistant metastatic breast cancer. Comparative studies of these drugs in this indication have been inconclusive with none of the agents emerging as definitely superior. Data is now available from randomised comparisons of all three drugs against tamoxifen as first-line treatment for advanced breast cancer. In the largest study using letrozole a clear statistically significant time to progression advantage for letrozole is apparent. The comparisons with tamoxifen and anastrozole are smaller, however a combined analysis of the hormone receptor-positive subsets of two similar trials shows a significant time to progression advantage for anastrozole. Preliminary data of a comparison between exemestane and tamoxifen demonstrated a borderline significant time to progression advantage for exemestane. Cross-trial comparisons do not suggest that major efficacy differences exist in this setting between these agents, although small but clinically relevant differences may exist.

### 3.3. Background – Exemestane

Exemestane is a very potent, orally active, selective and long-lasting steroidal, irreversible inactivator of aromatase. In *in vitro* studies exemestane appeared to be 2.8 and 156 times more potent than the steroidal compound formestane and the non-steroidal compound aminoglutethimide respectively in inhibiting human placental aromatase. *In vivo* studies of aromatase inactivation indicate that exemestane, by the oral route, is several times more potent than formestane. Exemestane has no noteworthy binding to oestrogen, progesterone, glucocorticoid or mineralocorticoid receptors and only a very low binding to the androgen receptor (Relative Binding Affinity (RBA) 0.2% of dihydrotestosterone (DHT)). However, its metabolite FCE 25071 (17-hydro-exemestane) was found to have a binding affinity to the androgen receptor (100-fold higher than that of exemestane and 0.28% that of DHT, Pfizer Ltd, data on file).

Early hormonal studies in breast cancer patients, using an oestrogen assay subsequently found to suffer from non-specific interactions of exemestane metabolites (Celite-RIA), indicated for exemestane a maximal inhibition of oestrogens up to 30% of baseline levels starting from doses of 2.5-5mg daily. However more recent results obtained, using a very specific and sensitive analytical method (HPLC-RIA), indicate that exemestane suppresses plasma oestrogens down to 6-11% of pre-treatment levels, thus showing an activity comparable to that observed with third-generation non-steroidal aromatase inhibitors such as letrozole, and significantly more pronounced than that of formestane.

Recent *in vitro* and clinical data on intratumoural and peripheral aromatase inhibition indicate that the drug is a potent inhibitor of the enzyme. *In vitro*, exemestane inhibits the aromatase

enzyme in human placenta, in adipose breast tissue and in tumour tissue, at concentrations of 1000nM, to 5%, 13% and 15% of the baseline values respectively. In patients, the drug inhibits peripheral aromatisation down to 2.2% of the baseline after 8 weeks of treatment with 25mg daily (Pfizer Ltd, data on file), which is considered to be the standard dose. These results are in line with or superior to the ones obtained with other non-steroidal aromatase inhibitors such as anastrozole or letrozole, and are consistent with the efficacy data thus far obtained in phase I and phase II studies.

